#### **5.4.2 AV7909 Compliance and Exposure**

AV7909 will be administered to all participants in all IP groups as a 0.5 mL IM vaccination in alternate arms on Days 8 and 23. Vaccinations will be administered in the clinic by authorized personnel in a controlled, clinical environment.

AV7909 exposure will be tabulated as the number and percentage of participants receiving each vaccination by treatment group for all vaccinations administered and for per-protocol vaccinations which are administered without any administration issues, e.g., incorrect product administered, incorrect dose of IP, incorrect route, missing previous dose, and outside the acceptable visit windows on Days 8 and 23( $\pm$  1 day). Shift of the first vaccination at Day 8 in Group 3 may be acceptable with consideration of subject overall vaccination and assessment schedules.

The subject listing of AV7909 vaccinations will be provided.

## **6 PK ASSESSMENT**

### **6.1 Serum Concentration Data**

Subjects with partial data will be evaluated on a case-by-case basis to determine if sufficient data are available for reliable estimation of PK parameters.

A listing of PK blood sample collection times as well as derived sampling time deviations will be provided.

### **6.2 Exclusion of Outliers**

Individual serum concentrations may be excluded from the analysis because they are erroneous or abnormal at the discretion of the pharmacokineticist following a review of available documentation (e.g., bioanalytical report, validation report) and communication with the sponsor. Any such exclusion will be clearly listed in the study report along with justification for exclusion.

Entire serum concentration-time profiles for a participant may be excluded following review of available documentation (e.g., bioanalytical report, validation report, and protocol deviation log) and communication with the sponsor. However, results of analysis with and without the excluded profiles may be presented in the study report. Any such exclusion will be clearly listed in the study report along with justification for exclusion.

Any excluded data will be flagged in the individual data listings.

### 6.3 Non-Quantifiable and Missing Concentrations

If a concentration value is below the lower limit of quantification (<LLOQ), which is 10 ng/mL for the ciprofloxacin assay and 100 ng/mL for the doxycycline assay:

- Individual concentration listings in the CSR should list these concentrations as “<LLOQ”.
- For the calculation of concentration summaries and plotting mean and individual concentration-time profiles, concentration values <LLOQ are treated as “zero”.

For purpose of calculating PK parameters, pre-dose concentrations <LLOQ, missing pre-dose values (Day 4 Group 1A and Day 2 Group 2A, only), and concentrations prior to the first quantifiable concentration that are <LLOQ are set to “zero”. A value <LLOQ occurring after  $C_{max}$ , that is embedded between two quantifiable points will be treated as missing for PK parameter calculation. Values <LLOQ occurring at the end of the collection interval (after the last quantifiable concentration value) will be set to “zero” to allow for calculation of  $AUC_{0-12h}$ . For calculation of  $AUC_{0-inf}$ , trailing zero values are treated as missing by Phoenix WinNonlin. If there are more than two consecutive <LLOQ concentrations after  $C_{max}$ , all concentrations after that may be treated as missing after pharmacokineticist review of available documentation (e.g., bioanalytical report, validation report).

For Handling of missing data for  $AUC_{0-inf}$  and  $AUC_{0-12h}$  calculation is described below in Section 6.4.

### 6.4 PK Parameters

Where possible, the PK parameters in [Table 3](#) for ciprofloxacin and doxycycline will be derived from the concentration-time data by non-compartmental techniques using actual elapsed time from dosing. If the actual PK sampling time is missing, but a valid concentration value has been measured, the scheduled protocol time may be used for the calculation of derived PK parameters.

Any anomalous concentration values observed at predose for single dose PK days will be identified in the clinical study report and used for the computation of PK parameters. Pharmacokinetic parameters will be computed irrespective to whether the anomalous concentration exceeds 5% of the observed maximum concentration ( $C_{max}$ ). If the anomalous predose concentration is greater than 5% of  $C_{max}$ , the PK parameters for the affected subject profile will be calculated and reported in the listing but excluded from statistical summaries and analyses. Similarly, PK concentrations for the affected profile will be excluded from statistical summaries.

Non-compartmental PK parameter calculations will be performed using Phoenix® WinNonlin® 8.0 or higher (Certara Company, Princeton, New Jersey, United States) or SAS version 9.4 or higher. Graphics may be prepared using the same versions of SAS, or Phoenix WinNonlin, or with SigmaPlot 12.5, or higher (Systat Software, Inc., San Jose, California, United States).

**Table 3 Ciprofloxacin and Doxycycline PK Parameters**

Variable	Definition
$C_{max}$	Maximum observed serum concentration
$t_{max}$	Time of maximum observed serum concentration
$t_{1/2}$	Half-life (calculated as $\ln 2 / K_{el}$ )
$K_{el}$	Apparent elimination rate constant; a minimum of 3 data points in the regression interval will be required for determination
$AUC_{0-12h}$	Area under the serum concentration-time curve (12 hours)
AUMC	Area under the first moment curve
$AUC_{0-inf}$	Area under the serum concentration-time curve extrapolated to infinity
MRT	Mean residence time

The linear-up/log-down trapezoidal summation will be used for calculation of AUC parameters.  $AUC_{0-inf}$  will only be calculated if  $K_{el}$  can be estimated. If  $K_{el}$  cannot be estimated due to missing data or an undetermined terminal phase,  $AUC_{0-inf}$  will not be calculated. The reliability of estimation of  $K_{el}$  and hence the PK parameters  $AUC_{0-inf}$  and  $t_{1/2}$  will be also be evaluated using diagnostic parameters (adjusted Rsq, time interval of the log-linear regression to determine  $K_{el}$ , percentage of  $AUC_{0-inf}$  obtained by extrapolation). If the adjusted Rsq is  $<0.800$ , then the  $K_{el}$ -related parameters  $AUC_{0-inf}$  and  $t_{1/2}$  will only be listed but not included in summary statistics. Any exclusions will be documented in the clinical study report.

$AUC_{0-inf}$  will only be calculated for single-dose serial PK days; for steady-state, only  $AUC_{0-12h}$  (i.e.,  $AUC_{0-tau}$ ) will be reported.

For calculation of  $AUC_{0-12h}$ , if the  $t=12h$  sample is missing or collected outside of the protocol-specified window of  $\pm 15$  min,  $AUC_{0-12h}$  will be determined to a nominal time point of 12 hours using interpolation or extrapolation (if  $K_{el}$  can be estimated; trailing BLQ values are to be set to missing in that case). For extrapolation, if  $K_{el}$  cannot be estimated due to missing data or an undetermined terminal phase,  $AUC_{0-12h}$  will not be calculated. Interpolation will not be performed if the subsequent concentration is  $<LLOQ$  and  $AUC_{0-12h}$  will not be calculated.

For multiple-dose profiles, if the concentration at time of dosing is missing then the concentration will be set to equal the concentration at the end of the dosing interval (assuming linear PK and steady-state conditions). For multiple-dose profiles with missing data at the end of the dosing interval for which interpolation/extrapolation is not possible, the missing concentration will be set to the pre-dose value to allow for calculation of  $AUC_{0-12h}$ .

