4.3.3. Doxycycline

The doxycycline dose (100 mg), dosing schedule [twice a day (q 12 hr)] and route of administration [by mouth (po)] being used in this study are those that would be used for PEP in the event of inhalation exposure to anthrax. As with ciprofloxacin, doxycycline administration will occur on an intermittent daily rather than a continuous daily dosing schedule for the same reason this approach is used for ciprofloxacin. This schedule will provide the required single dose and steady state PK dosing regimens needed and, in addition to achieving the needed steady-state concentrations before and after vaccination, is designed to achieve the immunogenicity end-points while restricting the antibiotics administered to the minimum required to achieve these ends.

However, since the half-life of doxycycline is considerably longer than that of ciprofloxacin (15-16 hours after a single dose and 22 or more hours after multiple doses compared to 3-7 hours for ciprofloxacin), participants in Group 2 will receive a few more doses of antibiotic than those in Group 1. This is because we believe more days of dosing will be required to achieve steady state. Thus, Group 2 will receive seven days of dosing with doxycycline compared to five days used for ciprofloxacin before tests for steady state are applied.

Doxycycline will also be administered in three courses that will be used both by site staff for in-clinic visits and by participants when they are at home. The format of the courses in terms of number of tablets and when participants will receive each course will be described in the Pharmacy Manual.

The doxycycline dosing periods were chosen because they have been shown to have an effect on humoral immunity in mice {Woo et al, 1999} and to affect post-vaccination cell-mediated immunity in swine {Pomorska-Mól et al. 2014}, suggesting it could also affect the antibody response to AV7909. The intermittent dosing schedule was chosen in the hopes of minimizing any adverse effects from doxycycline.

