8.1.4.2. Group 2A: Day 2 – Pre-vaccine Single Dose Doxycycline PK Session

1. Provide a non-dairy breakfast 30 to 60 min prior to dosing; provide a light lunch and a light dinner/snack over the course of the day.
2. Assess vital signs (seated/semi-recumbent blood pressure, heart rate, respiratory rate and temperature).
3. Collect blood sample for doxycycline t=0 concentration determination prior to administration of AM dose of doxycycline.
4. Administer AM dose of doxycycline following blood sample collection for t=0 antibiotic concentration determination and record time of administration in the source document and the eCRF; ensure the participant remains semi-recumbent for two hours after dosing and continues with a light activity level throughout the day.
5. Blood samples for doxycycline PK assessment are to be collected at the following time points: 0.25, 0.5, 0.75, 1, 1.5, 2, 2.5, 3, 4, 5, 6, 8, 10 and 12 hours post-dose (± 5 min through hr 4, then ± 15 min thereafter). The exact time of sample collection is to be recorded in the source document and eCRF.

AV7909 Anthrax Vaccine

IND 014451

Protocol EBS.AVA.210, Version 3.0 (28 October 2019)

6. Administer doxycycline dose (100 mg po) in the clinic after the final 12-hour doxycycline PK sample has been collected and 12 hours after morning dose (± 30 min), record exact time of administration in the source document and the eCRF.
7. Record any AEs reported.
8. Conduct a symptom-directed PE in response to any AEs reported.
9. Prior to being discharged from the clinic, participants will:
 - Be informed about the dietary and lifestyle precautions required when taking doxycycline (see [Section 5.3](#)).
 - Review the instructions on the use of the antibiotic e-diary to record compliance for the antibiotic doses (see [Section 8.3.5.1](#) e-diary).

Any participant who does not have or who does not wish to use their own personal device to access the e-diary will at this time be supplied a hand-held device by the site.

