8.1.4.13. Group 2A: Day 38: – Post-vaccine Steady-State Doxycycline PK Session

1. Provide a non-dairy breakfast 30 to 60 min prior to dosing; provide a light lunch and a light dinner/snack over the course of the day.
2. Assess vital signs (seated/semi-recumbent blood pressure, heart rate, respiratory rate and temperature).
3. Collect blood sample for doxycycline t=0 concentration determination prior to administration of AM dose of doxycycline.
4. Administer AM dose of doxycycline (100 mg po) following blood sample collection for t=0 concentration determination; ensure the participant remains semi-recumbent for two hours after dosing and continues with a light activity level throughout the day.
5. Blood samples for doxycycline PK assessment are to be collected at the following time points: 0.25, 0.5, 0.75, 1, 1.5, 2, 2.5, 3, 4, 5, 6, 8, 10, and 12 hours post-dose (± 5 min through hr 4 then ± 15 min).
6. Record any reported AEs.
7. Record concomitant medications.
8. Retain doxycycline supply; dose administered before PK session is the final dose.
9. When the participants are discharged from the clinic, they will be reminded to return to the clinic in seven days (nominally Day 51) for the final study visit.
10. Participants should also be reminded that they should still avoid strenuous sports and the sun and use sunscreens until the Day 51 Final In-clinic Study Visit.

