8.4.2. Doxycycline

On days with PK sessions (Days 2, 8, 32 and 38), blood samples for measurement of doxycycline concentrations will be collected at 0.25, 0.5, 0.75, 1, 1.5, 2, 2.5, 3, 4, 5, 6, 8, 10 and 12 hours post dose (± 5 min through hr 4, then ± 15 min thereafter).

Blood samples for determination of doxycycline pre-dose or trough concentrations will be collected on Days 2, 3, 4, 5, 6, 7 and 8 and on 32, 33, 34, 35, 36, 37 and 38 prior to administration of the morning doxycycline dose.

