## 6.5 PK Analyses

All PK analyses will be conducted based on the PK Population. All PK data listings will be presented based on the Safety Population.

PK concentration data will be summarized by study day and nominal time. The trough concentrations will be summarized by study day. The summary statistics for concentration data will include n, arithmetic mean, SD, median, minimum, maximum, and coefficient of variation (CV%).

PK parameters in **Table 3** will be summarized by study day. Summary of  $t_{max}$  will include n, median, minimum, and maximum only. For other PK parameters, n, arithmetic mean, SD, median, minimum, maximum, coefficient of variation (CV%), geometric mean, and geometric CV% will be presented.

The CV% is computed as:

$$CV\% = 100 \times (SD/Mean).$$

The geometric mean is computed as:

$$\text{Geometric mean} = \exp(\text{arithmetic mean of log transformed data}).$$

The geometric CV% is computed as:

$$CV\% \text{ geometric mean} = (\text{sqrt}(\exp(\text{variance for log transformed data}) - 1)) \times 100.$$

Individual as well as arithmetic mean concentration-time profile plots for serum concentration and trough concentrations will be presented in linear and semi-logarithmic scale.

The scatter plots of individual and geometric mean values for  $AUC_{0-12h}$  and  $C_{max}$  for ciprofloxacin and doxycycline will be presented for single dose and steady state profiles. The scatter plots of individual and geometric mean values for the ratio of  $AUC_{0-12h}$  and  $C_{max}$  will be presented for single dose and steady state profiles.

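### Doxycycline is sampled for less than one of its stated half-lives, and the SAP's only terminal-phase cut-off (adjusted Rsq) favours short half-lives and does not cover Kel, AUMC or MRT

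*SAP*

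**What the plan says.** Protocol 4.3.3 gives the doxycycline half-life as "15-16 hours after a single dose and 22 or more hours after multiple doses compared to 3-7 hours for ciprofloxacin". Protocol 8.4.2 sets the doxycycline samples on Days 2, 8, 32 and 38 at "0.25, 0.5, 0.75, 1, 1.5, 2, 2.5, 3, 4, 5, 6, 8, 10 and 12 hours post dose".

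Nothing later can serve as washout. On Day 2 the instruction is "Administer doxycycline dose (100 mg po) in the clinic after the final 12-hour doxycycline PK sample has been collected", and Days 8 and 32 follow the same pattern (Protocol 8.1.4.5 and 8.1.4.9). On Day 38 the "dose administered before PK session is the final dose", but the listed samples still end at 12 h (Protocol 8.1.4.13).

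SAP 6.4 and its Table 3 plan Cmax, tmax, t1/2, Kel, AUC0-12h, AUMC, AUC0-inf and MRT for both antibiotics, with AUC0-inf on single-dose days only. For Kel, "a minimum of 3 data points in the regression interval will be required for determination". Reliability is to be judged by "diagnostic parameters (adjusted Rsq, time interval of the log-linear regression to determine" Kel, and the percentage of AUC0-inf extrapolated). The only number attached is "If the adjusted Rsq is $<0.800$ , then the $K_{el}$ -related parameters" AUC0-inf and t1/2 are listed and left out of summary statistics.

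Under SAP 6.5, "PK parameters in Table 3 will be summarized by study day", and every parameter except tmax receives the full set of descriptive statistics.

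**The concern.** A terminal slope read from less than one half-life is weakly determined. Adjusted Rsq is a poor filter for it, because at a given noise level a flat line has a lower Rsq than a steep one. Slow profiles then tend to fail and steep ones, whether truly steep or steep by noise, tend to pass.

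The rule also names only AUC0-inf and t1/2. Table 3 defines t1/2 as ln 2/Kel, so a profile can lose its t1/2 from the summary while its Kel stays in. Whether AUMC and MRT depend on Kel cannot be told, because AUMC has no upper limit and MRT has no formula.

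At stake are the descriptive doxycycline tables before and after vaccination. Filtering is by profile, so the Day 2 and Day 32 summaries of t1/2 and AUC0-inf may also cover different participants.

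**Working it through.** The documents state no figure to reproduce here. Half-lives, sampling times and rules come from the sections cited above. Absorption rate (ka), residual CV, between-participant spread and slope-selection method are not in the documents and are assumptions.

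**1. Sampling span in half-lives**, 12/t1/2:
- doxycycline: 12/15 = 0.80, 12/16 = 0.75, 12/22 = 0.55
- ciprofloxacin: 12/3 = 4.0, 12/7 = 1.7

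**2. Share of single-dose AUC0-inf beyond 12 h.** With instant absorption it is 2^(-12/t1/2): 2^(-12/15) = 57% and 2^(-12/16) = 59.5%. With one-compartment first-order absorption and k = ln 2/t1/2, the share is (e^(-12k)/k - e^(-12ka)/ka) / (1/k - 1/ka). For ka 0.5-2 per h this gives 59% (15 h, ka 2) to 65% (16 h, ka 0.5). The overall range is 57-65%. For ciprofloxacin it is 6-11% at 3 h and 31-38% at 7 h.

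**3. Why Rsq favours steep slopes.** From 8 to 12 h doxycycline falls only 1 - 2^(-4/15) = 17% or 1 - 2^(-4/16) = 16%. Take the last three points (8, 10, 12 h), where the sum of squared time deviations is 8. With three points, adjusted Rsq = 1 - 2(1 - Rsq), so passing 0.800 needs Rsq of at least 0.90, that is 8b² ≥ 9 × SSE, where b is the slope of log concentration. With SSE at its expectation (σ², one degree of freedom):
- σ = 0.05: |b| ≥ 3 × 0.05/√8 = 0.053, so estimated t1/2 ≤ ln 2/0.053 = 13.1 h
- σ = 0.10: |b| ≥ 0.106, so estimated t1/2 ≤ 6.5 h

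SSE varies widely between profiles, so this shows direction, not a pass rate.

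**4. Simulation.** 3,000-4,000 single-dose profiles per scenario on the protocol times: median true t1/2 15.5 h, 20% between-participant spread, ka about 1 per h, best adjusted-Rsq slope from at least three points after Cmax, then the 0.800 rule.

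| Assumed residual CV | Profiles passing | Median t1/2 kept | Median t1/2 dropped | Kept t1/2 within 20% of truth | Geometric mean of kept AUC0-inf / truth |
|---|---|---|---|---|---|
| 5% | 81% | 14.4 h | 20.9 h | 56% | 1.00 |
| 10% | 44% | 11.5 h | 17.4 h | 34% | 0.90 |
| 15% | 31% | 9.2 h | 15.0 h | 21% | 0.80 |

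Two further runs with different settings gave kept medians of 14.9 and 15.1 h at 5% and 12.0 and 11.8 h at 10%. The shortfall from 15.5 h is therefore 0.4-1.1 h at 5% and 3.5-4.0 h at 10%. Using the last four or five points instead gave 14.7 and 14.9 h (5%) and 11.5 and 12.1 h (10%).

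**5. Ciprofloxacin, same method.** At true half-lives of 4 and 7 h and 5-10% CV, 95-100% of profiles pass and kept medians are 3.9-4.0 h and 6.5-7.0 h. The rule does little harm there.

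**6. Coverage of the rule.** Kel, AUMC and MRT are in Table 3 and in the SAP 6.5 summaries, but not among the parameters removed when Rsq fails.

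**The case against.** The strongest reply is that nothing inferential depends on these parameters. The primary and secondary equivalence analyses use AUC0-12h and Cmax (SAP 6.5.1 and 6.5.2), and Kel enters AUC0-12h only when the 12 h sample is missing or out of window. This stands. A reader might infer that the doxycycline equivalence conclusion is at risk; the documents do not support that. Nor does anything show a bias that differs before and after vaccination, since the sampling times are the same.

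The SAP also has safeguards: derivation where possible, a three-point minimum, no AUC0-inf when the terminal phase is undetermined, documented exclusions, and two further named diagnostics. It would be wrong to say that it ignores extrapolation and regression interval. It names both but gives neither a limit nor a consequence.

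Other stronger readings also fail:
- **The parameters cannot be estimated at all.** At 5% CV the kept median is within about 1 h of truth and mean AUC0-inf is unbiased. They are unreliable, to a degree set by noise that the documents do not give.
- **The extrapolated share at 22 h matters.** That is the multiple-dose half-life, and AUC0-inf is calculated on single-dose days only.
- **Steady-state MRT is wrong by a known amount.** That needs a formula the SAP does not state. The supportable point is that the definition is missing.
- **A general limit would cure it, for example two half-lives spanned and at most 20% extrapolated.** Neither figure is in the documents, and at 7 h two half-lives is 14 h, longer than the session. With ciprofloxacin half-lives assumed uniform over 3-7 h, such a rule cuts passing profiles from about 100% to about 20% and lowers the median t1/2 from 4.8-4.9 h to 3.7-3.8 h against a true 5.0 h. It would create in ciprofloxacin the selection it is meant to remove.

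**Conclusion.** The point holds as a defect in the descriptive doxycycline analysis. From the documents' own half-lives and sampling times, 12 h covers 0.75-0.80 of a single-dose half-life and more than half of AUC0-inf is extrapolated. The 57% floor needs only the stated half-lives and instant absorption; the 65% upper end assumes ka of 0.5 per h.

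The direction of the Rsq selection follows from how Rsq behaves on a shallow slope and was the same in every doxycycline scenario. Its size, roughly 0.5-4 h below a true 15.5 h, rests on the assumed 5-10% residual CV and the slope-selection method. The omission of Kel and the undefined AUMC and MRT rest on the SAP text alone. This should be corrected before the tables are produced, but it does not threaten the trial's conclusions.

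**What to change.** In SAP 6.4 and 6.5:

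1. For doxycycline, list Kel, t1/2, AUC0-inf and any AUMC or MRT extrapolated to infinity, each with percent extrapolated and regression interval, and leave them out of summary statistics. Describe the profile by Cmax, tmax, AUC0-12h and trough.
2. For both antibiotics, apply the adjusted Rsq exclusion to Kel and to any Kel-dependent AUMC or MRT, as well as to t1/2 and AUC0-inf.
3. State the upper limit of AUMC and the MRT formula. Do not report AUMC0-12/AUC0-12 as MRT on steady-state days.
4. Do not impose two-half-life or 20% limits on ciprofloxacin.

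Protocol 10.5.1.1 (Table 11) says that these parameters will be summarised by study day, and the synopsis lists them for both antibiotics. Either align that text or record the change as a documented deviation from the protocol's planned analysis. The cost is wording in two documents and fewer summarised doxycycline parameters. No sample, visit, endpoint or test changes.
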